3.8.2 Secondary Efficacy Endpoints

3.8.2.1 mRSS

The mRSS is a measure of skin thickness rated with scores ranging from zero (0; normal) to three (3; severe skin thickening) across 17 different sites. The total score is the sum of the individual skin scores in the 17 body areas (e.g., face, hands, fingers; proximal area of the arms, distal area of the arms, thorax, abdomen; proximal area of the legs, and distal area of the legs, feet), giving a range of 0-51 units. A negative change from baseline demonstrates improvement.

MRSS total score, change from baseline, percent improvement will be summarized as a continuous endpoint at all scheduled assessment visits.

The change from baseline and percent improvement in mRSS total score will be analyzed using the MMRM model. In addition, the change from baseline and percent improvement in mRSS total score will be analyzed using the ANCOVA model. Missing data will not be imputed.

3.8.2.2 PFTs

Onset/progression of ILD will be evaluated by the effect of belumosudil compared to placebo in the change in predicted FVC, which is based on institutional standards and will be measured as part of PFTs, including FEV1, FVC, DLco, TLC, and RV.

FVC (%) and change from baseline will be summarized as a continuous endpoint at all scheduled assessment visits. The change from baseline in FVC (%) will be analyzed using the MMRM model. In addition, the change from baseline will be analyzed using the ANCOVA model. Missing data will not be imputed.

FEV1, FVC, DL_{CO}, TLC, RV and their change from baseline will be summarized as a continuous endpoint in subjects with ILD at screening.

3.8.2.3 Physician Global Assessment

Physician global assessment is physician's assessment of patient's overall health during the last week based on a VAS of 0 (Extremely Poor)-100 (Excellent). A positive change from baseline demonstrates improvement.

Physician global assessment score, change from baseline, percent improvement will be summarized as a continuous endpoint at all scheduled assessment visits.

The change from baseline and percent improvement in physician global assessment score will be analyzed using the MMRM model. In addition, the change from baseline and percent improvement in physician global assessment score will be analyzed using the ANCOVA model. Missing data will not be imputed.

3.8.2.4 Patient Global Assessment

Patient global assessment is patient's assessment of their overall health during the last week based on a VAS of 0 (Extremely Poor)-100 (Excellent). A positive change from baseline demonstrates improvement.

Patient global assessment score, change from baseline, percent improvement will be summarized as a continuous endpoint at all scheduled assessment visits.

The change from baseline and percent improvement in patient global assessment score will be analyzed using the MMRM model. In addition, the change from baseline and percent improvement in patient global assessment score will be analyzed using the ANCOVA model. Missing data will not be imputed.

3.8.2.5 SHAQ-DI

SHAQ-DI includes the general HAD-DI assessment and 6 scleroderma-specific Visual Analog Scale (VAS) items to explore the impact of participant's disease. The general HAD-DI assessment includes 8 sections: dressing, arising, eating, walking, hygiene, reach, grip, and activities. The 6 VAS items will be rated separately in scale of a 0–100 millimeters [mm], with higher scores indicating more severe disease. The 6 items are: 1) pain, 2) intestinal disease, 3) breathing problem, 4) Raynaud syndrome, 5) finger ulcers, and 6) overall disease. A negative change from baseline demonstrates improvement.

SHAQ-DI total score, each of the 6 VAS scores and their change from baseline, percent improvement will be summarized as a continuous endpoint at all scheduled assessment visits.

The change from baseline and percent improvement in each SHAQ-DI score will be analyzed using the MMRM model. In addition, the change from baseline and percent improvement in patient global assessment score will be analyzed using the ANCOVA model. Missing data will not be imputed.

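### Percent improvement in the SHAQ-DI VAS items is modelled by MMRM although a zero baseline is allowed, where it is undefined, and near zero it is unstable

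*SAP*

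**What the plan says.** For SHAQ-DI, SAP 3.8.2.5 states: "The change from baseline and percent improvement in each SHAQ-DI score will be analyzed using the MMRM model". The scores are listed just before: "SHAQ-DI total score, each of the 6 VAS scores and their change from baseline, percent improvement will be summarized". Apart from pain, the VAS items are "2) intestinal disease, 3) breathing problem, 4) Raynaud syndrome, 5) finger ulcers, and 6) overall disease". Each is scored 0–100 mm, higher is worse, and missing data are not imputed. The ANCOVA sentence in that section names the patient global assessment, so as written only the MMRM applies to SHAQ-DI.

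The two globals are treated alike, by MMRM and ANCOVA. For the physician global (SAP 3.8.2.3): "The change from baseline and percent improvement in physician global assessment score will be analyzed using the MMRM model". For the patient global (SAP 3.8.2.4): "The change from baseline and percent improvement in patient global assessment score will be analyzed using the MMRM model". Both run 0–100, but there 0 is the worst state and a positive change is improvement.

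The SAP gives no formula or sign for percent improvement and no rule for a zero or very low baseline. SAP 3.1.6 covers only a missing baseline. The rank fallback in SAP 3.1.4.4 is for the CRISS score alone.

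**The concern.** A percentage change needs a denominator kept away from zero. The entry criteria provide that for mRSS (15 to 35) but not for SHAQ-DI, its VAS items or the globals. On an item such as finger ulcers, 0 simply means that the symptom is absent.

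Three consequences follow for the VAS items:

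- **Undefined values.** A subject starting at 0 has no percent improvement at any visit and drops out of that model without any stated rule. The percent and absolute-change results then describe different sets of subjects, and any symptom that first appears on study is invisible on the percent scale.
- **Unstable values.** A few subjects with small non-zero baselines can dominate an arm mean and the residual variance.
- **A one-sided subset within an arm.** One secondary objective compares Week 52 with baseline in subjects randomised to belumosudil. Dropping those who start a VAS item at 0 removes people who can only stay the same or worsen.

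**Working it through.** **Inputs from the documents.** 60 subjects, 20 per arm (SAP 3.1.3); VAS items and globals scored 0–100 (SAP 3.8.2.3 to 3.8.2.5); mRSS 15 to 35 at entry (Protocol 3.4). The plan states no figure for percent improvement, so there is nothing of its own to reproduce.

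**Formula (assumed, as the SAP gives none).** For a VAS item, percent improvement = 100 × (baseline − follow-up) / baseline. For a global, 100 × (follow-up − baseline) / baseline.

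**Step 1: what the ratio does.** The same 10-point change on a 0–100 scale gives:

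| Baseline | Size of percent change |
|---|---|
| 0 | undefined |
| 1 | 1000% |
| 2 | 500% |
| 5 | 200% |
| 10 | 100% |
| 50 | 20% |
| 80 | 12.5% |

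- VAS item, 2 to 12 mm: 100 × (2 − 12)/2 = -500%. Compared with no change in that subject, the mean of a 20-subject arm moves by 500/20 = 25 points.
- VAS item limits: improvement cannot exceed +100%; worsening from 1 to 100 mm is 100 × (1 − 100)/1 = -9900%.
- Globals are the mirror image: worsening stops at -100% and improvement can reach +9900%.
- Contrast, mRSS: a 5-unit change is 5/35 = 14% to 5/15 = 33% over the eligible range.

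**Step 2: how often a value is undefined.** Let p be the share of subjects at 0 on an item. It is not in the documents, so it is assumed. P(at least one of 60) = 1 − (1 − p)^60.

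| p | Expected at zero, of 60 | P(at least one) |
|---|---|---|
| 1% | 0.6 | 45% |
| 5% | 3 | 95% |
| 10% | 6 | over 99% |

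**Step 3: cost in precision (illustrative simulation).** Assumptions: 20 against 20, one follow-up visit, ANCOVA on baseline as a single-visit stand-in for the MMRM, a 15-point effect, a 15-point SD of change, two-sided 0.05.

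| Score and assumed baseline | Power, absolute change | Power, percent improvement |
|---|---|---|
| VAS, right-skewed, no added zeros | 78% | 52% |
| VAS, right-skewed, 10% added zeros | 77% | 48% |
| VAS, right-skewed, 30% added zeros | 73% | 39% |
| VAS, centred at 50 | 86% | 81% |
| Global, centred at 50 | 84% | 76% |
| Global, low and skewed, 2% added zeros | 85% | 51% |

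The median SD of percent improvement on a VAS item was about 38 points with the baseline centred at 50 and about 93 to 101 points with the skewed baseline.

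**Step 4: false positives.** With no treatment effect and a right-skewed VAS baseline (mean 25, SD of change 15, 0 to 30% added zeros), the percent analysis rejected about 3 to 4% of the time at a nominal 5%. It errs on the conservative side, so the damage is lost precision.

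**The case against.** The strongest reply is that little hangs on these models. The protocol synopsis defines these secondary outcomes as change from baseline; percent improvement is added by the SAP. Absolute change is modelled for every one of these scores, CRISS is built from absolute changes, and sample size is not driven by hypothesis testing. The continuous summaries include the median, minimum and maximum, so outliers would be seen. All of this stands and limits the weight of the point. It does not make a model of an undefined ratio sound.

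Four stronger readings are tempting, and the documents do not support them:

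- **The exclusion favours belumosudil over placebo.** It depends on a pre-dose value and applies to all randomised arms alike. It narrows the population but does not by itself favour an arm.
- **The same bias direction holds for the globals.** There 0 is the worst state, so a subject at 0 can only stay the same or improve. Exact zeros may also be rarer. What carries over is the instability at low baselines.
- **The percent models would produce false positives.** Step 4 points the other way under the inputs assumed.
- **The SHAQ-DI total behaves like the VAS items.** Neither document states its range or scoring steps, so that it can be 0 is an assumption. The VAS case does not need it.

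It is also fair to say that deletion is not the only cure. A defined formula, sign and zero-baseline rule with descriptive reporting would also serve.

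**Conclusion.** The point holds for the six VAS items on the text alone: the planned MMRM is applied to a quantity that is undefined at an allowed baseline and unstable just above it, with no rule to handle either case. The result is lost precision and a subset that differs from the absolute-change analysis. Only in the within-belumosudil Week 52 comparison does dropping zero baselines tilt a VAS result towards apparent improvement.

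The size depends on baseline distributions that the documents do not give. Under the assumed ranges, the loss of power runs from about 5 percentage points (86% to 81%, baseline centred at 50) to about 34 (73% to 39%, skewed baseline with 30% added zeros). The globals share the instability at low baselines but not the direction of bias.

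Severity is low: a worthwhile tidy-up of exploratory secondary analyses that leaves the primary endpoint untouched.

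**What to change.** - **SHAQ-DI scores (SAP 3.8.2.5).** Remove percent improvement from the MMRM and rely on absolute change adjusted for baseline, which SAP 3.1.4.4 already describes. No SHAQ-DI ANCOVA needs deleting, since that sentence names the patient global. If it is corrected to SHAQ-DI, limit it to absolute change.
- **Globals (SAP 3.8.2.3 and 3.8.2.4).** Remove percent improvement from the MMRM and ANCOVA, or report it only descriptively, as median and quartiles, with a stated formula, sign and zero-baseline rule.
- **mRSS (SAP 3.8.2.1).** Percent improvement can stay for comparisons from the randomisation baseline, where entry requires at least 15. That floor does not cover the open-label baseline that SAP 3.1.6 resets for former placebo subjects, so the SAP should say which baseline is meant.

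The cost is an SAP text change and fewer tables, with no new data. The downside is the loss of percent-scale model estimates for these scores.

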3.8.2.6 HRCT

Changes in lung fibrosis for patients with ILD at screening will be assessed using HRCT. Pure Ground-Class Opacity, Pulmonary Fibrosis and Honeycombing were recorded for each lung and three lung zones. They are recorded categorically for the amount detected, ranging from Absent to >75%. These will be summarized and change from baseline will be compared between treatment groups.

3.8.2.7 Treatment Emergent Adverse Events

Treatment emergent adverse events at Week 24 will be compared between treatment groups and placebo for subjects with dcSSc at baseline.

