2.2 SECONDARY OBJECTIVES

- To assess the CRISS for each group at Week 52
- To evaluate the efficacy of belumosudil compared to placebo at Week 24 for:
 - o mRSS
 - o FVC
 - Physician Global Assessment
 - o Patient Global Assessment
 - Scleroderma Health Assessment Questionnaire—Disability Index (SHAQ-DI)
- To evaluate the efficacy of belumosudil at Week 52 compared to baseline for subjects randomized to belumosudil for the parameters in the bullet above
- To assess changes in lung fibrosis, via high resolution computerized tomography (HRCT), performed at baseline, Weeks 24 and Week 52 only in subjects with ILD at screening
- To assess pharmacokinetics (PK) of belumosudil by sparse sampling of belumosudil on of Weeks 4 and 8 (i.e., Days 29 and 57) immediately prior to belumosudil dosing and 3 hours post-dose
- To assess the safety of belumosudil compared to placebo in subjects with dcSSc by examining the percentage of subjects with TEAEs (CTCAE v5.0) in subjects with dcSSc

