4.3 TREATMENT ASSIGNMENT

All subjects in the study will be double-blinded for the first 28 weeks and open-label for another 24 weeks.

Subjects will be randomized 1:1:1 to receive belumosudil 200 mg QD (Group 1), belumosudil 200 mg BID (Group 2), and matched placebo (Group 3) for the first 28 weeks. After unblinding, the subjects in Group 1 and 2 will continue on the same belumosudil dose whereas the subjects in the placebo group will be re-randomized to one of the belumosudil doses (200 mg QD or 200 mg BID) in 1:1 fashion. This unblinding will be done as each subject reaches 28 weeks.

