2.2 Study Design

KD025-209 is a Phase 2, placebo-controlled, double-blinded, randomized, multicenter trial in subjects with dcSSc with an open-label extension. The study schematic is shown below in Figure 1.

Subjects who have signed an Institutional Review Board (IRB)/ Independent Ethics Committee (IEC)-approved informed consent form and met all of the inclusion and do not meet all of the exclusion criteria will be enrolled. A total of 60 subjects will be randomized into 3 groups (1:1:1) to receive orally administered belumosudil 200 mg QD (n = 20), belumosudil 200 mg BID (n = 20), or matched placebo (n = 20) for 28 weeks. The study will be double-blinded for the first 28 weeks followed by an open-label extension of 24 weeks. After unblinding, the subjects in Group 1 and 2 will continue on the same belumosudil dose whereas the subjects in the placebo group will be re-randomized to one of the belumosudil doses (200 mg QD or 200 BID) in 1:1 fashion.

Efficacy will be assessed throughout the 52-week dosing period using CRISS, mRSS, PFTs, physician global assessment, SHAQ-DI.

[figure not shown]

Figure 1 KD025-209 Study Schema

be on a stable dose for at least 6 months prior to screening

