2.4 Treatment Descriptions

The treatment groups will be described below and used for different analysis.

KQD: KD025 200mg QD for the first 28 weeks

KBID: KD025 200mg BID for the first 28 weeks

PBO: Placebo for the first 28 weeks

KQD/KQD: KD025 200mg QD for the first 28 weeks and KD025 200mg QD from week 28 to 52.

KBID/KBID: KD025 200mg BID for the first 28 weeks and KD025 200mg BID from week 28 to 52.

K: KD025 200mg for the first 28 weeks

PBO/KQD: Placebo for the first 28 weeks and KD025 200mg QD from week 28 to 52.

PBO/KBID: Placebo for the first 28 weeks and KD025 200mg BID from week 28 to 52.

KQD_C: KD025 200mg QD for the first 28 weeks combined with subjects that switched from placebo to KD025 200mg QD from week 28 to 52.

KBID_C: KD025 200mg BID for the first 28 weeks combined with subjects that switched from placebo to KD025 200mg BID from week 28 to 52.

K_C: KD025 200mg for the first 28 weeks combined with subjects that switched from placebo to KD025 200mg from week 28 to 52.

All KD025 200mg QD: KD025 200mg QD for the first 52 weeks combined with subjects that switched from placebo to KD025 200mg QD from week 28 to 52.

All KD025 200mg BID: KD025 200mg BID for the first 52 weeks combined with subjects that switched from placebo to KD025 200mg BID from week 28 to 52.

All KD025: KD025 200mg for the first 52 weeks combined with subjects that switched from placebo to KD025 200mg from week 28 to 52.

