3 STATISTICAL METHODS

3.1 General Methods

3.1.1 Analysis Periods

The analysis will be split into three separate periods.

- The Double-Blinded Period analysis will be the period from week 0 to week 24.
- The Double-Blinded Period (0 week 28) will be the period from week 0 to week 28.
- The Combined Double-Blinded Period and Open-Label Period will be the period from week 0 to week 52.

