3.9.1 Adverse Events

AEs will be coded using the MedDRA dictionary (Version 22.0 or higher). TEAEs are any AEs occurring or worsening in severity after the first administration of study medication. All AEs (including SAEs) will be graded using the 5-point CTCAE V5.0 scale (mild, moderate, severe, life threatening, or death). Causality with study treatment will be classified as: definitely related; probably related; possibly related; unlikely related; not related.

The number (N) and percentage (%) of patients who experienced at least one TEAE will be summarized by dose group, including tabulation by:

- SOC and PTs within each SOC in decreasing total frequency
- PT in decreasing total frequency
- SOC, PTs, and maximum severity
- SOC, PTs, and relationship to study drug

These analyses will be repeated for Grade ≥3 TEAEs, SAE, TEAEs leading to dose modification, and AE leading to study drug discontinuation.

Subject listings will be provided for AEs, SAEs, AEs resulting in study drug discontinuation and deaths. Time to onset and duration of AEs will be included in listings, along with action taken and outcome.

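### The only named comparison of adverse events with placebo stops at Week 24, four weeks before randomised, blinded dosing ends

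*SAP*

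**What the plan says.** SAP 3.8.2.7, within the secondary efficacy endpoints, reads: "Treatment emergent adverse events at Week 24 will be compared between treatment groups and placebo for subjects with dcSSc at baseline". It names no test.

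The surrounding text points to 28 weeks.
- SAP 2.2: "The study will be double-blinded for the first 28 weeks followed by an open-label extension of 24 weeks". Protocol 4.3 adds: "This unblinding will be done as each subject reaches 28 weeks".
- The safety objective in Protocol 2.2 is "To assess the safety of belumosudil compared to placebo in subjects with dcSSc by examining the percentage of subjects with TEAEs", with no week attached. The neighbouring efficacy objective does carry Week 24.
- SAP 3.1.1 gives two double-blind periods. For the first, "The Double-Blinded Period analysis will be the period from week 0 to week 24"; the second "will be the period from week 0 to week 28". A third runs to Week 52.
- SAP 2.4 defines the three randomised arms (KQD, KBID, PBO) over the first 28 weeks.

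For the general TEAE tables, SAP 3.9.1 says: "The number (N) and percentage (%) of patients who experienced at least one TEAE will be summarized by dose group". It specifies counts and percentages and no exposure-adjusted rate. The TEAE window opens at the first dose of study medication and has no stated end. SAP 2.4 lists 14 treatment groupings and does not say which analysis uses which. One of them is "All KD025: KD025 200mg for the first 52 weeks combined with subjects that switched from placebo to KD025 200mg from week 28 to 52".

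**The concern.** Randomised, blinded dosing is the only part of the trial in which belumosudil can be compared with a concurrent placebo arm. With 20 subjects per arm there is little such data, and this is the first belumosudil study in this disease. Week 24 is the efficacy time point, and the documents give no safety reason for ending the TEAE comparison there.

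The secondary issue is that group and period are left open in 3.9.1, so they could be chosen after the data are seen. A placebo subject's first study medication is placebo, so an event that starts on open-label belumosudil still falls in a window opened by placebo. SAP 3.1.6 resets the baseline for these switchers, but nothing resets their TEAE window. A crude percentage from a group followed for up to 52 weeks would also be hard to read beside a placebo column that covers 28.

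**Working it through.** **Inputs from the documents.** 60 subjects, 20 per arm; 28 blinded weeks; 24 open-label weeks; placebo subjects re-randomised 1:1 at Week 28 (SAP 2.2). Background event rates are not given, so they are assumed below and shown as a range.

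**1. The plan's own figure.** Protocol 9.9 claims more than 90% probability of at least one affected subject at a 14% rate and more than 80% at 10%, with 20 per dose group. Using 1 - (1 - p)^20:
- p = 0.14: 1 - 0.86^20 = 95.1%
- p = 0.10: 1 - 0.90^20 = 87.8%

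Both statements hold.

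**2. What the Week 24 limit leaves out.** 60 x 4 = 240 of 60 x 28 = 1,680 planned subject-weeks, or 14.3%.

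**3. What including it gains.** Take an event affecting 10% by Week 24 at constant hazard: h = -ln(0.9)/24 per week.
- By Week 28: 1 - exp(-28h) = 11.6%
- Chance of at least one case in 20: 1 - 0.9^20 = 87.8% at Week 24; 1 - (1 - 0.1157)^20 = 91.4% at Week 28

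If the 10% is instead reached by Week 28, the two chances are 83.6% and 87.8%. In expected first-event subjects per arm, the gain is about 0.3 at a Week 28 rate of 10% and 1.0 at 50%.

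**4. The pooled groups, if read beside placebo.** Assume no drug effect, constant hazard, no dropout and all placebo subjects switching. With p the rate by Week 28, the rate by week t is 1 - (1 - p)^(t/28).
- All KD025 = (40 x rate at 52 + 20 x rate at 24)/60; mean exposure (40 x 52 + 20 x 24)/60 = 42.7 weeks
- K_C = (40 x rate at 28 + 20 x rate at 24)/60; mean exposure 26.7 weeks

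| Placebo, Week 28 (assumed) | Rate at 24 | Rate at 52 | All KD025 | Excess (points) | K_C | Difference (points) |
|---|---|---|---|---|---|---|
| 10% | 8.6% | 17.8% | 14.7% | +4.7 | 9.5% | -0.5 |
| 20% | 17.4% | 33.9% | 28.4% | +8.4 | 19.1% | -0.9 |
| 30% | 26.3% | 48.4% | 41.1% | +11.1 | 28.8% | -1.2 |
| 50% | 44.8% | 72.4% | 63.2% | +13.2 | 48.3% | -1.7 |

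For All KD025 (60) against placebo (20) at Week 28, the chance that a two-sided Fisher test at 0.05 falsely shows a belumosudil excess is 11.1% at a 30% background rate and 13.5% at 50%. With equal windows it is 1.8% at either rate.

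**5. Choosing the rate.** Dividing subjects with the event by total exposure does not cure this. At the 50% rate, All KD025 has 40 x 0.724 + 20 x 0.448 = 37.9 expected subjects over 2,560 weeks = 0.0148 per week. Placebo has 10 over 560 = 0.0179. The ratio is 0.83, a false deficit. If each subject's time stops at the first event, the same model gives equal expected rates.

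**The case against.** The strongest reply is that little is lost. SAP 3.9.1 has no Week 24 cut-off, a Week 0-28 period is pre-specified, and 3.8.2.7 is one sentence in a section whose other placebo contrasts are also set at Week 24. The study is exploratory, and the protocol's detection target at a 10% rate is met either way. This stands as a limit on size. A reader might infer that the last four blinded weeks are discarded from the safety evidence. The documents do not support that: the weeks are absent from one named comparison and may appear in the general tables.

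A reader might also infer that the SAP will set pooled belumosudil percentages over 24 to 52 weeks against placebo. No section assigns All KD025 to a TEAE table or contrasts it with placebo. The one specified comparison uses the same limit in every arm, so it creates no exposure imbalance. The _C groups combine 28 and 24 weeks and give no false excess.

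The excess figures also depend on full exposure and constant hazard. In the sponsor's earlier psoriasis trial only 27.3% completed treatment (Protocol 1.4.1.3). Early-clustered events would also shrink the excess. SAP 3.7 summarises treatment duration and 3.9.1 lists time to onset, so unequal exposure would be visible.

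What remains is that no text reserves the 28-week window for the placebo comparison or rules out a misleading table.

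**Conclusion.** The point holds as a modest, specific mismatch. The only named TEAE comparison with placebo ends at Week 24, while randomised, blinded dosing, the SAP's arm definitions and one of its analysis periods run to Week 28. The omission of 14.3% of planned controlled exposure is arithmetic on the design and assumes that all subjects stay on treatment. The detection gain of about 4 percentage points rests on constant hazard and the assumed 10% rate.

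The secondary point is conditional. The SAP leaves the group and period of its TEAE tables open. If an All KD025 column were read against 28 weeks of placebo, a false excess of about 5 to 13 points would be expected for background rates of 10% to 50%, under the assumptions in step 4. This describes a reading that the SAP does not prevent, not one that it plans.

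**What to change.** 1. Change SAP 3.8.2.7 to compare TEAEs for KQD, KBID and PBO from first dose to the end of blinded dosing, before the first open-label dose. Keep Week 24 as a supportive cut if wanted.
2. In SAP 3.9.1, state the treatment grouping and analysis period for each TEAE table.
3. For any group that includes open-label data, count TEAEs in switchers from their first belumosudil dose. Beside the percentage, report first events per 100 patient-years at risk, with time censored at the first event. Make no contrast with placebo.

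The cost is minor SAP wording and one extra derived rate. No new data are needed: AE onset dates and dosing dates are already collected.
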